**Special Attention**

Patients who wish to continue with ixazomib after completion of week 56 can continue on with therapy with ixazomib single agent. Rituximab will not be continued post week 56.

End of study biopsy and MRD testing is required.

Medications	C1D1	C1D8	C1D15	C1D21	C2 and Beyond
Rituximab	X	X	X	X	Rituxan to continue C3D1, with each cycle D1
Ixazomib	X	X	X		Continue days 1, 8 and 15 of each cycle.
TLS Assessment A	X	X	X	X	Continue days 1, 8 and 15 of each cycle.
Physical Exam	X				
CBC	X	X	X	X	
CMP	X	X	X	X	

- A. Patients should be assessed for risk and should receive appropriate prophylaxis for TLS, including hydration and anti-hyperuricemics. Monitor blood chemistries and manage abnormalities promptly. Interrupt dosing if needed. Employ more intensive measures (intravenous hydration, frequent monitoring, hospitalization) as overall risk increases

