#### Ixazomib Administration

All protocol-specific criteria for administration of study drug must be met and documented before drug administration. Study drug will be administered or dispensed only to eligible patients under the supervision of the investigator or identified subinvestigator(s). Patients should be monitored for toxicity, as necessary, and doses of ixazomib should be modified as

needed to accommodate patient tolerance to treatment; this may include symptomatic treatment, dose interruptions, and adjustments of ixazomib dose (see Section 6.3).

Capsules of ixazomib will also be referred to as study drug. Study drug will be supplied by Millennium as capsules of 2.3-, 3.0- and 4.0 mg ixazomib.

The prescribed administration of ixazomib doses in this study is 4 mg ixazomib in a 28 day cycle.

Patients should be instructed to swallow ixazomib capsules whole, with water, and not to break, chew, or open the capsules. Ixazomib should be taken on an empty stomach (no food or drink) at least 1 hour before or at least 2 hours after food. Each capsule should be swallowed separately with a sip of water. A total of approximately 8 ounces (240 mL) of water should be taken with the capsules.

Missed doses can be taken as soon as the patient remembers if the next scheduled dose is 72 hours or more away. A double dose should not be taken to make up for a missed dose. If the patient vomits after taking a dose, the patient should not repeat the dose but should resume dosing at the time of the next scheduled dose.

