**Dosage adjustments for hematologic toxicity are outlined in Table 6-2.**

**Table 6-2 Ixazomib Dose Adjustments for Hematologic Toxicities**

Criteria	Action
Within-Cycle Dose Modifications	

 
• If platelet count <math>\leq 30 \times 10^9/L</math> or ANC <math>\leq 0.50 \times 10^9/L</math> on a ixazomib dosing day (other than Day 1)
 
	
 
• Ixazomib dose should be withheld.
 
• Complete blood count (CBC) with differential should be repeated at least every other day until the ANC and/or platelet counts have exceeded the prespecified values (see Section 6.3.1) on at least 2 occasions.
 
• Upon recovery, ixazomib may be reinitiated with 1 dose level reduction.
 

Dose Modifications for Subsequent Treatment Cycles	

 
• Delay of > 2 weeks in the start of a subsequent cycle due to lack of toxicity recovery as defined in Section 6.3.1.
 
• ANC <math>< 1.0 \times 10^9/L</math>, platelet count <math>< 50 \times 10^9/L</math>
 
	
 
• Hold ixazomib until resolution as per criteria Section 6.3.1.
 
• Upon recovery, reduce ixazomib 1 dose level.
 
• The maximum delay before treatment should be discontinued will be 3 weeks or at the discretion of the PI.
 

Dose Modifications for Subsequent Treatment Cycles	

 
• All hematologic toxicities
 
	
 
• For hematologic toxicity that occurs during a cycle but recover in time for the start of the next cycle,:                             
 
○ If dose was reduced within the cycle, start the next cycle at that same dose.
 
○ If due to toxicity timing, i.e., after Day 15 dosing thus a dose reduction was not required at that point in the cycle, reduce ixazomib by 1 dose level at the start of that cycle.
 
○ Do not reduce the dose both within a cycle and at the start of the cycle for the same most severe toxicity.
 
 
 

Treatment modifications due to ixazomib-related AEs are outlined in Table 6-3.

**Table 6-3 Ixazomib Treatment Modification (Delays, Reductions, and Discontinuations) Due to Adverse Events (Non-Hematologic Toxicities)**

Adverse Event (Severity)	Action on Study Drug	Further Considerations
Peripheral Neuropathy:		

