## **6.10 Storage, Handling, and Accountability**

Upon receipt at the investigative site, ixazomib should remain in the blister and carton provided until use or until drug is dispensed. The container should be stored at the investigative site as per

labeled instructions (do not store above 30°C or 86°F, do not freeze). Ensure that the drug is used before the retest expiry date provided by Millennium. Expiry extensions will be communicated accordingly with updated documentation to support the extended shelf life.

In countries where local regulations permit, ixazomib capsules dispensed to the patient for take-home dosing should remain in the blister packaging and stored per labeled instructions as noted above until the point of use. The investigative site is responsible for providing the medication to the patient in the correct daily dose configurations. Comprehensive instructions should be provided to the patient in order to ensure compliance with dosing procedures. Patients who are receiving take-home medication should be given only 1 cycle of medication at a time. Patients should be instructed to store the medication per labeled instructions (not store above 30°C or 86°F, do not freeze) for the duration of each cycle. Patients should be instructed to return their empty blister packs to the investigative site, rather than discarding them. Reconciliation will occur accordingly when the patient returns for their next cycle of take-home medication. Any extreme in temperature should be reported as an excursion and should be dealt with on a case-by-case basis.

Ixazomib should be handled with due care. Patients should be instructed not to chew, break, or open capsules. In case of contact with broken capsules, raising dust should be avoided during the clean-up operation. The product may be harmful by inhalation, ingestion, or skin absorption. Gloves and protective clothing should be worn during cleanup and return of broken capsules and powder to minimize skin contact.

The area should be ventilated and the site washed with soap and water after material pick-up is complete. The material should be disposed of as hazardous medical waste in compliance with federal, state, and local regulations.

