**11.3 SCHEDULE OF STUDY ASSESSMENTS**

Days (+/-3d)	Screening A	C1D1	C2D1	C3D1	C4D1	C5D1	C6D1	C7D1	C8D1	C9D1	C10D1	C11D1	C12D1	C13D1	C14D1	C15D1+	EOS (+/- 7 days)
Informed consent, review inclusion/exclusion, general medical history B	X																
Vital signs, weight and height	X	X	X	X	X	X	X	X	X	X	X	X	X	X	X	X	X
ECOG and B symptoms C	X	X	X	X	X	X	X	X	X	X	X	X	X	X	X	X	X
Physical Exam D	X	X	X	X	X	X	X	X	X	X	X	X	X	X	X	X	X
12 lead ECG and ECHO E	X																
PET/CT or CT scan F	X				X F				X F				X F			X F	X F
Bone marrow biopsy/aspirate G	X				X G				X G							X G	X
MRD assessment H	X				X H				X H							X H	X
Tumor biopsy	X																X
CBC, CMP, and Hepatitis Testing i,j	X	X	X	X	X	X	X	X	X	X	X	X	X	X	X	X	X J

Days (+/-3d)	Screening A	C1D1	C2D1	C3D1	C4D1	C5D1	C6D1	C7D1	C8D1	C9D1	C10D1	C11D1	C12D1	C13D1	C14D1	C15D1	
Quantitative Immunoglobulins	X																
Pregnancy Test	X																

Footnotes Table of Assessments

- A. Perform within 28 days prior to cycle 1 day 1. Assessments performed as standard of care may be used for screening. *BIOPSY TISSUES* obtained up to 8 weeks prior to start of C1D1 can be used as long as we have enough tissue for analysis.
- B. Written informed consent form(s) must be signed by the patient before any study specific procedures are performed.
- C. B symptoms: Unexplained weight loss>10% over previous 6 months, fever (>38C) and/or drenching night sweats.
- D. Complete physical exam at screening, including cardiovascular, respiratory, abdominal, lymph node, skin ENT, extremities and endocrinological examination. Targeted physical exams at subsequent visits, limited to systems of clinical relevance, (i.e., cardiovascular, respiratory, lymph nodes, liver, and spleen), and dose systems associated with clinical signs/symptoms.
- E. Single 12-lead ECG and Echo is required at screening. If clinically significant abnormality is noted by the attending physician, a referral to cardiology will be made.

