- F. CT scans must include neck, chest, abdomen, pelvis and include oral and IV contrast. PET/CT performed at screening, at the end of Cycle 4, at the end of cycle 8, at the end of Cycle 15, and at the End of Study visit if not performed within the last 2 months. After Cycle 15, CT scans will be performed every 4 months. If PET/CT is performed and includes a CT scan of sufficient diagnostic quality and provides bidimensional nodal and liver and spleen measurements, an additional dedicated CT is not required at the time point. MRI may be used in place of CT at investigator's discretion.
- G. Bone marrow biopsies/aspirates at specified time points are mandatory (Screening, at the end of cycle 4, at the end of cycle 8, at the end of Cycle 15, and at the End of Study visit ) unless shown to be clear on previous examination by multi flow cytometry minimum sensitivity 10-4. \* If patient has progression on the study, we do require Bone marrow biopsy/aspiration at progression. For example, if week 9 imaging study shows clear progression beyond a reasonable doubt, we would like to perform a bone marrow biopsy/aspiration for end of study.
- H. Minimal residual disease assessment by ASO PCR in mantle cell lymphoma patients and flow cytometry. Peripheral blood will be collected from all patients as well as bone marrow aspirates in those patients required to undergo bone marrow aspirate and biopsy will be collected at Screening, at the end of cycle 4, at the end of cycle 8, at the end of cycle 15, and at the End of Study visit. Collect 20 mL's of blood in EDTA and 5 mL of a bone marrow aspirate in EDTA. Transport within 4 hours at room temperature to appropriate laboratory.

- I. Blood chemistry: Sodium, potassium, chloride, BUN, creatinine, glucose, calcium, total protein, albumin, AST, ALT, alkaline phosphatase, total bilirubin, LDH, phosphate, uric acid, magnesium and bicarbonate.

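### From Cycle 2 no blood count is scheduled on Day 8 or Day 15, although the within-cycle ixazomib hold rule depends on one

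*Combined protocol and SAP*

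**What the plan says.** The within-cycle row of Table 6-2 applies when platelets are ≤30 x10^9/L or ANC is ≤0.50 x10^9/L "on a ixazomib dosing day (other than Day 1". The dose is then withheld. Two further steps follow: "Complete blood count (CBC) with differential should be repeated at least every other day" until the counts recover, and "Upon recovery, ixazomib may be reinitiated with 1 dose level reduction". The row is not limited to Cycle 1.

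Section 6.2 gives ixazomib on Days 1, 8 and 15 of each 28-day cycle. The medication table under Special Attention in Section 11.3 repeats this for Cycle 2 onward ("Continue days 1, 8 and 15 of each cycle") and uses the same entry for the TLS assessment.

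Counts are scheduled in two places:

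- **Main grid, Section 11.3.** The row "CBC, CMP, and Hepatitis Testing" is marked at screening, Day 1 of each cycle and end of study. The grid has no Day 8 or Day 15 column.
- **Medication table.** CBC is marked on Days 1, 8, 15 and 21 of Cycle 1. Its cell for Cycle 2 and beyond is empty.

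Section 6.10 permits home dosing: "Patients who are receiving take-home medication should be given only 1 cycle of medication at a time".

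**The concern.** A rule that turns on the platelet count and ANC for a given dosing day can be applied only if a count is available for that day. After Cycle 1 the schedule stops ordering one, while the drug and the TLS assessment continue on Days 8 and 15.

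A full cycle of capsules can be handed out after the Day 1 check. From Cycle 3 rituximab is given on Day 1 only, so no infusion brings the patient in mid-cycle. A site working from the schedule could let a patient take a dose that Table 6-2 says to withhold. It would then also miss the repeat counts and the one-level dose reduction tied to that hold. Section 6.7 says that both thrombocytopenia and neutropenia may be severe.

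What is at stake is patient safety and correct dose modification. The primary endpoint is not affected. The effect on the maximum-grade toxicity table (Section 7.1.6) is limited, because Section 8.1.1 does not treat an abnormal laboratory value as an adverse event unless it alters treatment, needs intervention or is judged clinically significant.

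**Working it through.** The plan states no figure on this point, so the check is a direct count of doses against scheduled tests.

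**Inputs**

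- Dosing days: 1, 8 and 15 of each cycle (Section 6.2; medication table).
- Days governed by the hold rule: 8 and 15 (Table 6-2).
- Scheduled CBC: Day 1 of every cycle (main grid), plus Days 8, 15 and 21 of Cycle 1 (medication table).
- Visit window: ±3 days (main grid).
- Planned length: 12 cycles, with ixazomib allowed to continue afterwards (Section 6.2).

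**Formulas for c completed cycles**

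- All ixazomib doses: 3c
- Doses governed by the rule: 2c
- Doses with a CBC scheduled on the dosing day: c (the Day 1 doses) + 2 (Cycle 1 Days 8 and 15)
- Doses without one: 3c − (c + 2) = 2(c − 1), all of them Day 8 or Day 15 doses

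| Cycles | All doses | With CBC | Without CBC | Governed doses | Share of governed doses without CBC |
|---|---|---|---|---|---|
| 2 | 6 | 4 | 2 | 4 | 50.0% |
| 4 (week 16) | 12 | 6 | 6 | 8 | 75.0% |
| 12 | 36 | 14 | 22 | 24 | 91.7% |
| 14 (14 × 28 = 392 days, week 56) | 42 | 16 | 26 | 28 | 92.9% |

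**Visit window.** A Day 1 visit with ±3 days extends to Day 4 at the latest. The next cycle's Day 1 is Day 29, and its window opens on Day 26. Neither reaches Day 8 or Day 15, so the counts above are unchanged.

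**Could another ordered test supply the count?** Sections 6.3.2 and 6.3.3 and the TLS row call for blood chemistries at later doses. Footnote I of Section 11.3 defines that panel ("Blood chemistry: Sodium, potassium, chloride, BUN, creatinine, glucose, calcium, total protein, albumin, AST, ALT" and further chemistry items); it contains neither platelets nor ANC. A chemistry draw alone therefore cannot trigger the hold.

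**Does the Day 1 check cover it?** Section 6.4.1 lets a cycle start at platelets of 50,000/mm³ and ANC of 1,000/mm³. That is 50 − 30 = 20 x10^9/L above the platelet hold level and 1.0 − 0.5 = 0.5 x10^9/L above the ANC hold level. Two governed doses then follow before the next scheduled count, 28 days after the last. Table 6-2 also has a row for hematologic toxicity that arises within a cycle and has recovered by the next one; a Day 1 count cannot see such an event.

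**The case against.** The best case against is that other text already leads a site to the count. Section 6.2 says: "All protocol-specific criteria for administration of study drug must be met and documented before drug administration". The Table 6-2 threshold is reasonably read as one of those criteria. Section 6.7 calls for regular counts and further testing under standard practice. The TLS footnote asks for risk assessment, and the high and medium TLS risk categories use the lymphocyte count. If the TLS chemistries are followed, blood is already drawn before these doses, so a wholly unchecked home dose would usually mean that other required assessments had been missed as well.

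Two further points are fair. The empty CBC cell is weak evidence by itself: the CMP and physical examination cells beside it are also empty, yet both continue elsewhere in the protocol. And 22 of 24 assumes 12 completed cycles in a relapsed or refractory population; patients who progress early accrue fewer such doses, and none in Cycle 1.

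Much of this stands as mitigation. It does not close the gap. None of these sections names a CBC on Day 8 or Day 15 after Cycle 1. Section 6.7 says counts are monitored as the protocol sets out, which points back to the schedule with the omission. The chemistry draw provides the occasion but not the platelets or ANC. The conclusion does not rest on the empty cell alone, because the main grid independently has no mid-cycle column.

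**Conclusion.** The concern holds. From Cycle 2 the schedule does not order the count that the within-cycle hold rule needs. The size is 2(c − 1) of 2c governed doses: 22 of 24 over 12 cycles, with a range from 50% at two cycles to 93% at week 56.

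The count assumes that every dose falls due in each completed cycle; the documents give no expected number of cycles. It measures tests that are not scheduled. It says nothing about how many holds would be missed, which cannot be estimated from the documents. It is an omission, not a contradiction, and a careful site may draw the count anyway. Day 1 counts still gate each cycle. Section 6.7 refers to the Investigator's Brochure for further adverse event management, and that source was not available to check.

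It should be fixed, because a site that follows the schedule exactly could give doses that the protocol's own safety rule says to withhold, and the remedy is small.

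**What to change.** In the medication table of Section 11.3, fill the CBC cell for Cycle 2 and beyond with: CBC with differential before the Day 8 and Day 15 doses of each cycle, drawn with the chemistries already called for and reviewed before the dose is taken. All 24 governed doses over 12 cycles then have a scheduled count. The change does not capture falls in counts after Day 15.

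The cost is a protocol amendment to one cell and one extra tube at each Day 8 and Day 15 draw: up to 22 per patient over 12 cycles, 26 to week 56, and two per cycle after that while ixazomib continues. Expect a few more dose holds. Where the chemistry draw would not otherwise be done on site, each count may need an extra visit, up to two per cycle.

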11.4 Lugano Criteria 2014

Table 2. Revised Staging System for Primary Nodal Lymphomas		
Stage	Involvement	Extranodal (E) Status
Limited		
I	One node or a group of adjacent nodes	Single extranodal lesions without nodal involvement
II	Two or more nodal groups on the same side of the diaphragm	Stage I or II by nodal extent with limited contiguous extranodal involvement
II bulky*	II as above with “bulky” disease	Not applicable
Advanced		
III	Nodes on both sides of the diaphragm; nodes above the diaphragm with spleen involvement	Not applicable
IV	Additional noncontiguous extralymphatic involvement	Not applicable

NOTE. Extent of disease is determined by positron emission tomography-computed tomography for avid lymphomas and computed tomography for nonavid histologies. Tonsils, Waldeyer’s ring, and spleen are considered nodal tissue.
 
*Whether stage II bulky disease is treated as limited or advanced disease may be determined by histology and a number of prognostic factors.
		

Table 3. Revised Criteria for Response Assessment		
Response and Site	PET-CT–Based Response	CT-Based Response
Complete	Complete metabolic response	Complete radiologic response (all of the following)
Lymph nodes and extralymphatic sites	Score 1, 2, or 3* with or without a residual mass on 5PS† It is recognized that in Waldeyer’s ring or extranodal sites with high physiologic uptake or with activation within spleen or marrow (eg, with chemotherapy or myeloid colony-stimulating factors), uptake may be greater than normal mediastinum and/or liver. In this circumstance, complete metabolic response may be inferred if uptake at sites of initial involvement is no greater than surrounding normal tissue even if the tissue has high physiologic uptake	Target nodes/nodal masses must regress to $\leq 1.5$ cm in LDi No extralymphatic sites of disease
Nonmeasured lesion	Not applicable	Absent
Organ enlargement	Not applicable	Regress to normal
New lesions	None	None
Bone marrow	No evidence of FDG-avid disease in marrow	Normal by morphology; if indeterminate, IHC negative
Partial	Partial metabolic response	Partial remission (all of the following)
Lymph nodes and extralymphatic sites	Score 4 or 5† with reduced uptake compared with baseline and residual mass(es) of any size At interim, these findings suggest responding disease  At end of treatment, these findings indicate residual disease	$\geq 50\%$ decrease in SPD of up to 6 target measurable nodes and extranodal sites When a lesion is too small to measure on CT, assign 5 mm $\times$ 5 mm as the default value When no longer visible, 0 $\times$ 0 mm For a node > 5 mm $\times$ 5 mm, but smaller than normal, use actual measurement for calculation
Nonmeasured lesions	Not applicable	Absent/normal, regressed, but no increase
Organ enlargement	Not applicable	Spleen must have regressed by > 50% in length beyond normal
New lesions	None	None
Bone marrow	Residual uptake higher than uptake in normal marrow but reduced compared with baseline (diffuse uptake compatible with reactive changes from chemotherapy allowed). If there are persistent focal changes in the marrow in the context of a nodal response, consideration should be given to further evaluation with MRI or biopsy or an interval scan	Not applicable
No response or stable disease	No metabolic response	Stable disease
Target nodes/nodal masses, extranodal lesions	Score 4 or 5 with no significant change in FDG uptake from baseline at interim or end of treatment	< 50% decrease from baseline in SPD of up to 6 dominant, measurable nodes and extranodal sites; no criteria for progressive disease are met
Nonmeasured lesions	Not applicable	No increase consistent with progression
Organ enlargement	Not applicable	No increase consistent with progression
New lesions	None	None
Bone marrow	No change from baseline	Not applicable
Progressive disease	Progressive metabolic disease	Progressive disease requires at least 1 of the following PPD progression:
Individual target nodes/nodal masses	Score 4 or 5 with an increase in intensity of uptake from baseline and/or	An individual node/lesion must be abnormal with: LDi > 1.5 cm and Increase by $\geq 50\%$ from PPD nadir and An increase in LDi or SDi from nadir 0.5 cm for lesions $\leq 2$ cm 1.0 cm for lesions > 2 cm
Extranodal lesions	New FDG-avid foci consistent with lymphoma at interim or end-of-treatment assessment	In the setting of splenomegaly, the splenic length must increase by > 50% of the extent of its prior increase beyond baseline (eg, a 15-cm spleen must increase to > 16 cm). If no prior splenomegaly, must increase by at least 2 cm from baseline New or recurrent splenomegaly
Nonmeasured lesions	None	New or clear progression of preexisting nonmeasured lesions

(continued on following page)

**Table 3. Revised Criteria for Response Assessment (continued)**

Response and Site	PET-CT–Based Response	CT-Based Response
New lesions	New FDG-avid foci consistent with lymphoma rather than another etiology (eg, infection, inflammation). If uncertain regarding etiology of new lesions, biopsy or interval scan may be considered	Regrowth of previously resolved lesions A new node > 1.5 cm in any axis A new extranodal site > 1.0 cm in any axis; if < 1.0 cm in any axis, its presence must be unequivocal and must be attributable to lymphoma Assessable disease of any size unequivocally attributable to lymphoma
Bone marrow	New or recurrent FDG-avid foci	New or recurrent involvement

Abbreviations: 5PS, 5-point scale; CT, computed tomography; FDG, fluorodeoxyglucose; IHC, immunohistochemistry; LDi, longest transverse diameter of a lesion; MRI, magnetic resonance imaging; PET, positron emission tomography; PPD, cross product of the LDi and perpendicular diameter; SDi, shortest axis perpendicular to the LDi; SPD, sum of the product of the perpendicular diameters for multiple lesions.

\*A score of 3 in many patients indicates a good prognosis with standard treatment, especially if at the time of an interim scan. However, in trials involving PET where de-escalation is investigated, it may be preferable to consider a score of 3 as inadequate response (to avoid undertreatment). Measured dominant lesions: Up to six of the largest dominant nodes, nodal masses, and extranodal lesions selected to be clearly measurable in two diameters. Nodes should preferably be from disparate regions of the body and should include, where applicable, mediastinal and retroperitoneal areas. Non-nodal lesions include those in solid organs (eg, liver, spleen, kidneys, lungs), GI involvement, cutaneous lesions, or those noted on palpation. Nonmeasured lesions: Any disease not selected as measured, dominant disease and truly assessable disease should be considered not measured. These sites include any nodes, nodal masses, and extranodal sites not selected as dominant or measurable or that do not meet the requirements for measurability but are still considered abnormal, as well as truly assessable disease, which is any site of suspected disease that would be difficult to follow quantitatively with measurement, including pleural effusions, ascites, bone lesions, leptomeningeal disease, abdominal masses, and other lesions that cannot be confirmed and followed by imaging. In Waldeyer’s ring or in extranodal sites (eg, GI tract, liver, bone marrow), FDG uptake may be greater than in the mediastinum with complete metabolic response, but should be no higher than surrounding normal physiologic uptake (eg, with marrow activation as a result of chemotherapy or myeloid growth factors).

†PET 5PS: 1, no uptake above background; 2, uptake ≤ mediastinum; 3, uptake > mediastinum but ≤ liver; 4, uptake moderately > liver; 5, uptake markedly higher than liver and/or new lesions; X, new areas of uptake unlikely to be related to lymphoma.

Source: *Recommendations for Initial Evaluation, Staging, and Response Assessment of Hodgkin and Non-Hodgkin Lymphoma: The Lugano Classification*  
 Bruce D. Cheson, Richard I. Fisher, Sally F. Barrington, Franco Cavalli, Lawrence H. Schwartz, Emanuele Zucca, and T. Andrew Lister  
 Journal of Clinical Oncology 2014 32:27, 3059-3067
